7.5.1 Prior Medication

Prior medications will be summarized by WHO Drug Dictionary (December 2013) standard medication name, cohort, and treatment group. Prior medication will be listed. Prior AED medications will be summarized separately.

A prior medication will be defined as any drug that has a start date before the first dose date of study drug. Any medication that starts on the first dose date of study drug will not be considered prior. Medications with a completely missing start date will be considered prior.

Partial start dates will be used to determine if a medication is prior. Medications with a completely missing start date will be considered prior. If only a start month and year are present, then medications for which the month is before or the same as the first dose month will be

considered prior. If only the start year is present, then medications for which the start year is before or the same as the first dose year will be considered prior.

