9.3 Adverse Events

The summary of AEs (or SAEs) will be limited to treatment emergent adverse events (TEAEs). A TEAE is any AE (or SAE) occurring on or after administration of the first dose of study medication and before the end of study. An existing AE which worsens on or after administration of the first dose of study medication is also considered a TEAE. AEs will be tabulated by treatment and Overall, system organ class (SOC), and Preferred Term using the MedDRA v.16.0 coding system. The number and percentage of subjects with adverse events will be calculated for each cohort in each phase of the study, by treatment and overall, and in Cohort 1 DB phase, by dose and overall. Additional tables with AEs subset by severity and by relationship to drug as assessed by the investigator will also be presented. Subset listings will be

produced for adverse events that cause withdrawal and for SAEs. Any AE with completely missing start and end dates will be considered a TEAE.

All necessary information about an AE (onset, duration, severity, seriousness, causality to study drug, action taken, and outcome) should be documented by the investigator on the adverse event eCRFs (AE eCRFs). Minimum information required for each AE includes type of event, duration (start and end dates), severity, seriousness, causality to study drug, action taken, and outcome.

Severity of AEs will be graded by the Investigator using the following criteria as guidelines:

1. Mild: Nuisance, barely noticeable.
2. Moderate: Uncomfortable, troublesome symptoms not significantly interfering with daily activities or sleep.
3. Severe: Symptoms significantly interfere with daily activities or sleep.

The relationship of the AE to the study drug should be specified by the Investigator, using the following definitions:

1. Not Related: Concomitant illness, accident or event with no reasonable association with study drug.
2. Unlikely Related: The event has little or no temporal sequence from administration of the study drug, and/or a more likely alternative etiology exists.
3. Possibly Related: The event follows a reasonable temporal sequence from administration of study drug but which could also be explained by concurrent disease or other factors or medications.

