Adverse events will be summarized by treatment group and overall for each cohort and phase separately for subjects in the Safety Population. In Cohort 1 tables, AE's will be summarized by treatment, dose level, and overall for subjects in the Safety Population, adverse events of subjects pooled in Cohort 1 and Cohort 2 for each treatment phase will be summarized. The following AE tables will be generated:

- An overall summary of the number and percentage of subjects reporting AEs, serious SAEs, treatment-related AEs, AEs leading to treatment discontinuation and AEs leading to death
- AEs overall and by system organ class and preferred term
- AEs by maximum severity, overall and by system organ class and preferred term
- AEs by relationship to study treatment, overall and by system organ class and preferred term
- AEs with onset (or worsening) during titration + 1200 mg/day dose (weeks 1 to 5) and 1800 mg/d (weeks 6 to 9) by preferred term in Cohort 1 DB phase
- AEs with onset (or worsening) during titration phase and maintenance phase by preferred term in Cohort 2 DB phase
- AEs with onset (or worsening) during the de-escalation phase (time interval between Pre-Taper/Early Termination visit and Post-Taper Safety Follow Up visit) by preferred term in Cohort 1 and 2 OL phase

All AEs, SAEs, AEs leading to drug discontinuation and AEs leading to death will be listed.

Missing date will be imputed followed table describes how missing date information will be handled:

Partial Missing Start or Stop Date	Imputed Start Date	Imputed Stop Date
Missing month and day, and the year is present	January 1 of that year or first dose date if the year is the same as the year of first dose date	December 31 of that year
Missing day, but year and month are present	First day of that month or first dose date if the year and month are the same as the year and month of first dose date	Last day of that month
Missing month, but year and day are present	Missing month imputed as January	Missing month imputed as December

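### The partial-date table in SAP 9.3 can drop month-missing AEs from the TEAE tables and can place AEs that begin after the switch in the double-blind phase

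*SAP*

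**What the plan says.** SAP 9.3 gives three rules for an incomplete AE start date:

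- Row 1, month and day missing: "January 1 of that year or first dose date if the year is the same as the year of first dose date".
- Row 2, day missing: "First day of that month or first dose date if the year and month are the same" as those of first dose.
- Row 3, month missing but day and year known: "Missing month imputed as January", with no reference to first dose.

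The same section states: "The summary of AEs (or SAEs) will be limited to treatment emergent adverse events (TEAEs"). A TEAE is an event "occurring on or after administration of the first dose of study medication and before the end of study", or an existing one that worsens after first dose. It adds: "Any AE with completely missing start and end dates will be considered a TEAE".

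AEs are tabulated by treatment group, cohort and phase. Some tables are explicitly defined by onset: titration against maintenance in Cohort 2, and weeks 1 to 5 against weeks 6 to 9 in Cohort 1. All AEs are also listed.

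Protocol 9.4.5 and its Tables 1 and 2 move placebo subjects to ganaxolone on Day 64 (Cohort 1) or Day 99 (Cohort 2), and step Cohort 1 from 1200 to 1800 mg/d on Day 36. No row of the date table mentions any of these dates or the stop date.

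**The concern.** There are two separate gaps.

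First, row 3 lacks the protection that rows 1 and 2 have. A record with day and year known can be judged pre-treatment and leave the TEAE tables, while a record with no dates is kept. The better-documented event is treated less conservatively.

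Second, rows 1 and 2 always choose the earliest compatible date from first dose onward. If the known parts fit both sides of the switch, the event goes to double-blind. For a placebo subject this attributes an event that occurred on ganaxolone to placebo, in the comparison on which the safety assessment rests. Protocol 9.4.5 itself anticipates tolerability problems such as sedation or dizziness during the transition. The same gap affects the Cohort 1 dose-level table at Day 36.

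**Working it through.** The plan states no figure on this point, so there is none to reproduce. The three rows were applied exactly as written.

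**Inputs.** From the documents: Cohort 2 double-blind is Days 1–98, and open-label is Days 99–462 (week 66 × 7), with Day 478 (last full dose in Protocol Table 2) as a range check. Cohort 1 double-blind is Days 1–63 and open-label Days 64–427. Assumed, not in the documents: first-dose dates uniform over a 365-day year and onsets uniform over treatment.

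**Worked example, Cohort 2.** First dose on 16 March 2015; switch on Day 99 = 16 March + 98 days = 22 June 2015.

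| True onset | Known parts | Imputed date | Result |
|---|---|---|---|
| 28 June 2015 (Day 105) | month, year | 1 June (Day 78) | double-blind |
| 10 Aug 2015 (Day 148) | year | 16 March (Day 1) | double-blind |
| 10 May 2015 (Day 56) | day, year | 10 Jan 2015 | before first dose, not a TEAE |
| 10 Feb 2016 (Day 332) | day, year | 10 Jan 2016 (Day 301) | TEAE, open-label: correct |

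A year-only date in a later year can also go wrong. With first dose on 10 November 2015 (switch on 16 February 2016), a true onset of 10 August 2016 becomes 1 January 2016, which is Day 53 and double-blind.

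**Cohort 1 dose step.** With first dose on 16 March 2015, Day 36 is 16 March + 35 days = 20 April. A true onset of 25 April with the day missing becomes 1 April (Day 17), which falls in weeks 1 to 5 instead of weeks 6 to 9.

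**Enumeration** over every first-dose date and onset day:

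| Date record | Cohort 2 | Cohort 2, to Day 478 | Cohort 1 |
|---|---|---|---|
| Year only: open-label onsets placed in double-blind | 50.1% | 48.0% | 50.0% |
| Day missing: open-label onsets placed in double-blind | 4.0% | 3.9% | 4.0% |
| Month missing: double-blind onsets classed as pre-treatment | 82.2% | 82.2% | 87.1% |
| Month missing: open-label onsets classed as pre-treatment | 23.8% | 22.8% | 30.9% |
| Month missing: open-label onsets placed in double-blind | 22.2% | 21.3% | 15.1% |

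**When row 3 fails.** In Cohort 2, 91.4% of month-missing records are dated before first dose if the onset year is the first-dose year, and 0% if it is later. A separate simulation gave 92.2%. A rough check by hand: the share of same-year onset time that belongs to January first doses is 1 − (11/12)² = 16.0%. About half of that keeps an imputed date on or after first dose, and 100% − 8% = 92%.

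**When row 2 fails.** It fails only in the calendar month of the switch, where 94% of post-switch onsets are misplaced. For onsets in the 14-day Cohort 2 transition, take a 30-day month with the switch on a uniform day. Same-month pairs number 30 × 14 − (0 + 1 + … + 13) = 420 − 91 = 329. Of these, 14 belong to a switch on the 1st, where the imputed date is the switch date itself and the phase is right. The misplaced share is (329 − 14)/420 = 315/420 = 75%.

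**A first-dose floor in row 3 alone.** The loss of Cohort 2 double-blind onsets falls from 82.2% to 0%, but 23.8% + 22.2% = 46.0% of month-missing open-label onsets would then sit in double-blind. Both gaps need a rule.

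**The case against.** The strongest reply is that this is a narrow wording gap. Start and end dates are minimum required AE information (Protocol 10.5.2, SAP 9.3), and AEs are recorded at each visit, so partial dates may be few. A record with day and year but no month should be rarer still. Rows 1 and 2 never turn a post-dose event into a pre-treatment one. Row 2 errs only in the switch month. Assignment by onset is explicit for the by-period tables but only inferred for the overall phase tables. All of this stands. It limits the likely effect but does not make the assignments right.

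Three stronger readings are tempting, and the documents do not support them:

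- *Active treatment is made to look safer.* Row 3 drops records in both arms. Rows 1 and 2 also pull open-label events of the ganaxolone arm into double-blind ganaxolone, so double-blind counts rise in both arms. Only for placebo subjects is the treatment itself wrong, and the net direction is not shown. At the Cohort 1 step, the shift is between two ganaxolone doses.
- *On-treatment events disappear.* They leave the summary tables. SAP 9.3 still lists all AEs, SAEs, AEs leading to discontinuation and deaths.
- *SAP 7.5 and 7.5.1 are in conflict.* SAP 7.5 applies the same date table to AEDs, and 7.5.1 says "Any medication that starts on the first dose date of study drug will not be considered prior". But 7.5.1 has its own rule for partial start dates, and that specific rule can be read as deciding prior status.

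**Conclusion.** The point holds as two conditional errors. A month-missing AE with onset in the first-dose year is usually classed as pre-treatment (about 91–92%) and leaves the TEAE tables, against the SAP's own inclusive rule for undated events. A partial date that spans the switch is placed in double-blind, which for a placebo subject charges a ganaxolone-exposed event to placebo. The Cohort 1 step at Day 36 has the same gap.

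The percentages are per affected record and rest on uniform first-dose and onset dates. They are not effects on any AE rate. The documents do not say how many dates will be partial, so neither the absolute effect nor its net direction can be computed. The rules give demonstrably wrong assignments and are cheap to correct, so they should be corrected before unblinding.

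**What to change.** In SAP 9.3:

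(a) Row 3: if the onset year is the first-dose year and the January date precedes first dose, impute the first dose date and treat the event as a TEAE, unless the stop date shows that it ended before first dose. The imputed date settles TEAE status only; the recorded day stays in the listing.

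(b) If the known parts of the date are compatible with onset both before and after the start of open-label ganaxolone, or the Cohort 1 step to 1800 mg/d, assign the event to the later period. Make an exception when the stop date or an earlier visit record shows that it began before. Never override a known part of the date.

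The visit-record exception matters. A blanket rule dating every event after the last visit before it was recorded would push a late-reported double-blind event into open-label and could contradict a known month. Rule (b) can still move a true double-blind onset to open-label when nothing resolves the date, so the number of records it affects should be reported by arm.

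Optionally, add one sentence to SAP 7.5 saying that the partial-date rule in 7.5.1 governs prior status.

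The cost is SAP wording and programming, with no new assessments. The stated minimum AE fields do not include the visit of first recording, so check that the database holds it; if it does not, the exception rests on the stop date alone.

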9.4 Laboratory Evaluations

Laboratory data (including change from baseline) will be summarized using descriptive statistics by treatment and overall for each cohort and phase separately for subjects in the Safety Population. Laboratory data of subjects pooled in Cohort 1 and Cohort 2 for each treatment phase will be summarized. SI units will be used for both summarization and data listings.

Separate summary tables and listings will be produced for each laboratory test group (Hematology, Serum Chemistry, Urinalysis, and other tests: See Protocol Appendix 2: Clinical Laboratory Tests).

Hematology, Serum Chemistry, Urinalysis, and other tests will be summarized for baseline, each visit assessed, and for change from baseline by treatment group using descriptive statistics.

Low, normal, and high classifications will be applied according to the central lab's definitions to determine whether the worst laboratory test value within the visit window was below (low), within (normal), or above (high) its reference range. Shifts from baseline in low/normal/high classification for each parameter will be summarized by treatment group.

If there are multiple records within a visit window the last record will be used for summary tables, all results will be used for tables that assess maximum grade or toxicity, and included in data listings.

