Adverse events reported from Study 1042-0600 in at least 5% of subjects and >1.5 times more frequent in the ganaxolone group than the placebo group were dizziness (16.3 v. 8.3%), fatigue (16.3 v. 8.3%) and somnolence (13.3 v. 2.0%). The discontinuation rates due to adverse events between the ganaxolone and placebo groups in Study 1042-0600 were comparable, 7.1% and 6.1% respectively.

In Study 1042-0600 and in the ganaxolone development program overall, no clinically significant trends in changes from baseline electrocardiogram (ECG) recordings, vital signs, or physical or neurological examinations have been noted in the clinical studies,

and no mean changes from baseline in clinical labs have been identified. Transient increases in LFTs ($>3\times$ ULN) have been noted in less than 1% of subjects treated with ganaxolone. Serious adverse events (SAEs) reported in the ganaxolone epilepsy trials were considered by a Scientific Advisory Board to be usual for the population without any pattern attributable to ganaxolone. Profiles of the most frequently reported AEs have been consistent with the predicted pharmacology of the drug.

Due to the favorable tolerability profile of ganaxolone in Study 1042-0600 and its open-label extension, the current study is designed to further examine the safety, tolerability and efficacy of ganaxolone as adjunctive treatment of POS when administered BID at doses up to 1800 mg/day in a capsule formulation.

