 - d. Any Suicidal Behavior as classified by the Columbia Suicide-Severity Scale (C-SSRS) or a "yes" answer to question 4 and 5 in the Suicidal Ideation section of the C-SSRS. These patients should be referred to psychiatric evaluation immediately.
11. Any subject who has the following liver enzyme findings should be immediately contacted and instructed to stop the study drug or start down titration of the study drug

- a. ALT or AST > 8 x ULN
- b. ALT or AST >5 x ULN for more than 2 weeks
- c. ALT or AST > 5 x ULN and total bilirubin >2 x ULN
- d. ALT or AST >3 x ULN with the appearance of fatigue, nausea, vomiting, right upper quadrant pain or tenderness, fever, rash or eosinophilia

Patients with ALT or AST > 3 x ULN but <8 x ULN and no clinical signs and symptoms indicating liver dysfunction can, at the discretion of the investigator, continue the intake of study drug with close monitoring.

All patients who fall into either category (patients who must discontinue the study drug [a, b, c and d] and who may continue the study drug with close monitoring) must be brought back to the study center without any delay, the next day if possible, but no later than 72 hours after the study results have been received, for evaluation of the underlying cause and confirmatory laboratory testing. More frequent monitoring of the liver tests should be initiated.

Discontinuation decisions will be made at each participating site by the Site Principal Investigator. If feasible, the process of discontinuation should be discussed with the Medical Monitor. The decisions regarding the discontinuation of the investigational therapy, whether the study medication should be stopped immediately or tapered should be discussed with the Medical Monitor, but final decisions about the process will remain at the discretion of the Site Principal Investigator.

Subjects who are discontinued from the clinical investigation for any reason will not be replaced.

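### SAP 9.4 defines no by-arm count of liver tests by multiple of ULN, and its by-visit tables use the last record, usually the recheck after a high value

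*SAP*

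**What the plan says.** Protocol section 7 (Introduction) states that transient liver function test rises above 3 x ULN "have been noted in less than 1% of subjects treated with" ganaxolone. That section does not name ALT or AST, and it also reports no mean changes in clinical laboratory tests.

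Protocol 9.3.4.1, item 11, lists four findings that lead to stopping or tapering study drug: "ALT or AST > 8 x ULN"; "ALT or AST >5 x ULN for more than 2 weeks"; "ALT or AST > 5 x ULN and total bilirubin >2 x ULN"; and "ALT or AST >3 x ULN with the appearance of fatigue, nausea, vomiting, right upper quadrant pain or tenderness, fever, rash or eosinophilia". Subjects between 3 x and 8 x ULN without clinical signs may continue at the investigator's discretion. Both groups must return, the next day if feasible, "but no later than 72 hours after the study results have been received, for evaluation of the underlying cause and confirmatory laboratory testing". Liver tests are then monitored more often.

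SAP 9.4 plans three kinds of laboratory output:
- Descriptive statistics by visit. Under SAP 6.1 these include the maximum. The record rule is "If there are multiple records within a visit window the last record will be used for summary tables". The same sentence goes on to keep all results for tables of maximum grade or toxicity and for listings.
- Shift tables: "Shifts from baseline in low/normal/high classification for each parameter will be summarized by treatment group". The class comes from the worst value in the visit window, judged against the central laboratory's range.
- Data listings. Protocol 9.7.7 adds flags for critically significant changes, and the protocol synopsis adds listings of the most abnormal changes.

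Protocol 9.5.3 requires both the original and the repeat value in the eCRF. SAP 6.4 defines visit windows by the mid-points between consecutive scheduled visits.

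**The concern.** The protocol describes and manages liver findings in multiples of ULN, but no output defined in the SAP uses that scale. A reader of the tables could not see how many subjects per arm passed 3, 5 or 8 x ULN, or how many had raised transaminases and raised bilirubin together.

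The by-visit maximum is the one planned summary statistic that could show a peak as a number. It is taken from the last record in the window. Unscheduled repeats are required because a value was high, so the choice of record depends on the result: subjects with normal values keep their scheduled record, and subjects with a high value are usually represented by the recheck. Events this rare show up in counts and extremes, not in means.

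**Working it through.** The plan states no figure on this point, so there is none to reproduce. Three checks follow.

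**1. Can the shift tables separate the protocol's limits?** No. A worst value of 1.1 x ULN and one of 9 x ULN are both high. Exclusion criterion 19 allows entry with ALT or AST up to 3 x ULN, so a subject who enters at 2.5 x and rises to 9 x ULN is high at both points and shows no shift.

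**2. Does the recheck fall in the same window as the value that triggered it?** Inputs are the visit weeks in Protocol 9.5.5, the mid-point rule in SAP 6.4, the visit tolerances in Protocol 9.5.5 (±3 days for Visits 3 to 6, ±7 days later) and a recheck 1 to 3 days after the result. Laboratory turnaround is not given and is assumed to be 1 to 3 days. For Visits 3 to 6 the grid has 7 x 3 x 3 = 63 combinations. A recheck leaves the window when nominal day + visit offset + turnaround + recheck delay exceeds the window end.

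| Visit | Nominal day | Window end | Slack (days) | Rechecks leaving the window |
|---|---|---|---|---|
| Cohort 2, V3 | 14 | 35 | 21 | 0/63 |
| Cohort 2, V4 | 56 | 77 | 21 | 0/63 |
| Cohort 2, V5 | 98 | 105 | 7 | 4/63 (6%) |
| Cohort 2, V6 | 112 | 126 | 14 | 0/63 |
| Cohort 1, V3 | 7 | 21 | 14 | 0/63 |
| Cohort 1, V4 | 35 | 49 | 14 | 0/63 |
| Cohort 1, V5 | 63 | 66.5 | 3.5 | 36/63 (57%) |

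Cohort 1 V6 also gives 0/63, and Visits 7 to 9 in both cohorts give 0/135. At Cohort 2 Visits 3 and 4 the result hardly depends on the assumed turnaround: even with the visit 3 days late and the recheck 3 days after the result, 21 - 3 - 3 = 15 days remain for it. At Visit 5 the corresponding margins are 7 - 6 = 1 day (Cohort 2) and 3.5 - 6 = -2.5 days (Cohort 1).

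**3. Size.**
- Effect on a visit mean of replacing one subject's value by 1 x ULN among 178: from 4 x, (4 - 1)/178 = 0.017 x ULN; from 8 x, (8 - 1)/178 = 0.039 x ULN.
- Expected ganaxolone cases above 3 x ULN = 178 x p. The protocol gives only an upper figure of 1%, so p from 0.25% to 1% is an assumption. P(at least 1) = 1 - (1 - p)^178; P(at least 2) is the exact binomial tail.

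| Assumed rate p | Expected cases | P(at least 1) | P(at least 2) |
|---|---|---|---|
| 0.25% | 0.45 | 0.36 | 0.07 |
| 0.5% | 0.89 | 0.59 | 0.22 |
| 1% | 1.78 | 0.83 | 0.53 |

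**The case against.** The strongest reply is that the plan already has several safeguards. Shift tables use the worst value in the window, so the triggering value still counts there as high. All results feed the maximum grade or toxicity tables and the listings. Critical values are flagged. Laboratory abnormalities that the investigator judges clinically significant, or that need intervention, are recorded as adverse events (Protocol 10.5.2, SAP 9.3) and tabulated by arm. With about two cases or fewer expected in the ganaxolone arm, each can be read individually in the listings. The mock-ups are in a separate file (SAP 14) and the SAP appendices are not in the available text, so a toxicity table may be specified there.

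Much of this stands. A reader might infer that the last-record rule replaces every triggering value and hides the liver findings. The documents do not support that: the rule bears on by-visit descriptive statistics, not on shift tables or listings; some Visit 5 rechecks fall in the next window; and nothing guarantees that a recheck is lower than the trigger. A reader might also infer that by-visit means are materially biased. They are not, as the third check shows.

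The safeguards still leave a gap. Listings and flags are by subject and give no count by arm. Adverse event tables depend on investigator judgement, and a subject without clinical signs between 3 x and 8 x ULN may continue on drug without an event being recorded. The toxicity tables have no scale, parameters or layout in the available text, although SAP section 2 aims to specify outputs completely.

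**Conclusion.** The point holds in a limited form. The available SAP text defines no by-arm summary of ALT, AST or bilirubin on the scale the protocol uses for its own liver rules, and the low/normal/high shifts cannot stand in for one. The last-record rule adds a smaller problem: where the recheck is lower than the trigger, the peak usually drops out of the by-visit maximum. That is the expected pattern in Cohort 2, apart from about 6% of Visit 5 rechecks, and the exception is larger at Cohort 1 Visit 5 (57%). Both percentages rest on the assumed 1 to 3 day turnaround. The SAP also does not say plainly whether the last or the worst record governs each table. The conclusion about what is undefined is limited to the text available; the mock-ups could supply part of it. This is a reporting gap worth closing, not evidence that harm would be concealed.

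**What to change.** In SAP 9.4, add one descriptive table by arm, cohort and phase with the number and percent of subjects whose worst post-baseline value, over all scheduled and unscheduled records, exceeds:
- ALT or AST 3, 5 and 8 x ULN;
- total bilirubin 2 x ULN;
- both a transaminase limit and the bilirubin limit in the same subject, including the protocol's own pairing of ALT or AST above 5 x with bilirubin above 2 x ULN.

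State whether the paired elevations must come from the same sample or may occur at any time after baseline. These are tabulation bins only: they change no clinical rule, and they do not count subjects meeting the protocol rules that depend on duration or symptoms.

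For by-visit descriptive statistics, use the scheduled-visit record (or the worst in the window) instead of the last, and state which record rule governs which table. Either define the maximum grade or toxicity tables, with their scale, or replace that reference with the table above.

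The cost is SAP wording and one or two extra outputs from data already in the eCRF. Counts will be sparse and should be presented as descriptive, not as a powered comparison.
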